11.5 Notification of deaths

All deaths, including deaths deemed unrelated to the IMP, even if they occur earlier than expected will be reported to the Sponsor.

This report will be sent to the JRO as documented in Section 11.3 within 24 hours of the Chief or Principal Investigator (CI/PI) becoming aware of the death.

11.6 Reporting of SUSARs

The JRO will notify all SUSARs to the MHRA and the main REC using CIOMs form. The CIOMs form should be completed by the CI and PI at each site and sent to the JRO along with the Sponsor's SAE Recording and Reporting Form as described in Section 11.3 of the protocol. The

JRO will inform the MHRA and the main REC of fatal or life threatening SUSARs as soon as possible, but no later than 7 calendar days after the JRO receives and dates the SAE report form. Any additional information will be reported within 8 days of sending the first report.

The JRO must report all other SUSARs and safety issues to the MHRA and main REC, as soon as possible but no later than 15 calendar days after the JRO has first knowledge of the minimum criteria for expediting reporting.

11.7 The type and duration of the follow-up of subjects after AEs

Follow-up will continue for the duration of the study.

Any participant suffering an AE while an inpatient, will receive assessment, treatment and follow-up by the nursing and clinical care team, and as required by the study team, until clinical stability is resumed and/or the AE has resolved. Ongoing care and follow-up will be provided by the nursing and clinical team, with assistance of the study team as required.

A 24-hour contact number will be available for all patients and/or clinical staff to contact the study team if required.

Patients will be given advice to contact the study team (using a 24-hour contact number), or if need be, the ambulance service, should they suffer an AE following discharge. Depending on the nature of the reaction, advice may be given by telephone that no action is required; that the participant should seek urgent medical review (in which case the study team endeavour to make contact with the relevant receiving unit); that the participant should attend for early follow-up with the study team (and as appropriate, that the study treatment should be suspended). Follow-up will be provided by the study team and/or the participant's general practitioner (in liaison with the study team), with an intensity appropriate to the nature and severity of the adverse reaction.

The JRO will ensure that all SAE/Rs reported to Sponsor will be followed every 2 weeks until resolution, and in accordance with Sponsor's PV SOP.

11.8 Development Safety Update Reports (DSURs)

The CI will prepare the DSUR, according to the ICH Guideline E2F – "Note for guidance on development safety update reports". It will be reviewed by the Sponsor and when necessary be referred to an independent committee (i.e. Research Governance Safety Committee). The JRO will provide the main REC and the MHRA with the DSUR within 60 days of the anniversary of the CTA authorisation.

11.9 Annual Progress Reports (APRs)

The Chief Investigator will prepare the APR. It will be reviewed by the JRO and sent to the main REC within 30 days of the anniversary date on which the favourable opinion was given, and annually until the trial is declared ended.

11.10 Pregnancy

Metformin is not known to be harmful in pregnancy; animal studies do not indicate harmful effects with respect to pregnancy, embryonic or foetal development, parturition or postnatal development.³⁶ Although not licensed for this indication, the British National Formulary lists metformin as a treatment option for both pre-existing and gestational diabetes in pregnancy.³⁹ Consequently, it seems extremely unlikely that metformin presents significant hazards in relation to the unborn child. Moreover, the epidemiology of chronic obstructive pulmonary disease is such that participants are very unlikely to be of childbearing age; most patients with COPD are over 65-years-old.⁴

Nevertheless, the pregnancy risk of female patients of potentially childbearing age will be ascertained by establishing their menstrual history; past symptoms suggestive of menopause; and, as appropriate, contraceptive use. Women who are of childbearing age and who are fertile will be asked to use medically-effective contraceptive methods while they are enrolled in the study. They will be asked to stop taking the study medicine if their period is more than one week overdue or if they otherwise suspect they are pregnant, and to report this to the study team. The study treatment will be discontinued and details of the patient's involvement in the study will be passed to the relevant obstetric team, if the patient was assigned to active treatment. In view of animal data suggesting the absence of teratogenicity, in conjunction with the absence of clinical data suggesting teratogenicity in the face of considerable experience in its use (including in polycystic ovary syndrome as a means to improve fertility, and in diabetes in pregnancy), we do not propose to offer further follow-up to the offspring of a participant in this trial.

All pregnancies will be reported to the JRO using the Pregnancy Reporting Form and followed up in accordance with the JRO Pharmacovigilance SOP.

11.11 Reporting urgent safety measures

Regulation 30 of the Medicines for Human Use (Clinical Trials) Regulations 2004 [Statutory Instrument 2004/1031], as amended by Statutory Instrument 2006/1928 states "the Sponsor and the Investigator may take appropriate urgent safety measures in order to protect the subjects of a clinical trial against any immediate hazard to their health or safety. If measures are taken, the Sponsor shall immediately and in any event no later than 3 days from the date the measures are taken, give written notice to the MHRA and the relevant REC of the measures taken and the circumstances giving rise to those measures."

In order to prevent any delays in the reporting timelines the Sponsor has delegated this responsibility to the CI/PI. Therefore the CI/PI must report any urgent safety measures to the MHRA directly, and in parallel to the Sponsor.

Please refer to the following website for details on clinical trials safety reporting: <http://www.mhra.gov.uk/Howweregulate/Medicines/Licensingofmedicines/Clinicaltrials/Safetyreporting-SUSARSandASRs/index.htm>

11.12 Notification of serious breaches to GCP and/or the protocol

Any Protocol Deviations, Violations, Potential Serious Breaches and urgent safety measures will be recorded using Sponsor's Log issued during Sponsor's Trial/Site Initiation meeting/visit.

Regulation 29A of the Medicines for Human Use (Clinical Trials) Regulations 2004 [Statutory Instrument 2004/1031], as amended by Statutory Instrument 2006/1928, contains a requirement for the notification of "serious breaches" of GCP or the trial protocol:

(1) The Sponsor of a clinical trial shall notify the licensing authority in writing of any serious breach of

(a) the conditions and principles of GCP in connection with that trial; or

(b) the protocol relating to that trial, as amended from time to time in accordance with regulations 22 to 25, within 7 days of becoming aware of that breach.

(2) For the purposes of this regulation, a "serious breach" is a breach which is likely to effect to a significant degree

(a) the safety or physical or mental integrity of the subjects of the trial; or

(b) the scientific value of the trial.

The Sponsor will be notified immediately of any case where the above definition applies during the trial conduct phase. The sponsor's SOP on the Protocol Violation/Deviations and Serious Breaches will be followed.

12 Data management and quality assurance

12.1 Confidentiality

All data will be handled in accordance with the Data Protection Act 1998.

The Case Report Forms (CRFs) will not bear the subject's name or other personal identifiable data. The subject's initials, date of birth and trial identification number will be used for identification.

All data pertaining to identifiable persons shall be regarded as confidential. While a patient is enrolled in the study, and remains a hospital inpatient, data in relation to their nutritional assessment, administration of the study treatment (blinded), capillary glucose measurements and safety parameters, shall be available to the clinical team caring for the patient. This is because such data may be important to the patients' clinical care, and this may avoid unnecessary duplication.

12.2 Data collection tool

Case report forms (CRFs) will be designed and produced by the investigator. The final version will be approved by the Sponsor. All data will be entered legibly in black ink with a ball-point pen. If an error is made, the error will be crossed through with a single line in such a way that the original entry can still be read. The correct entry will then be clearly inserted, and the alterations will be initialled and dated by the person making the alteration. Overwriting or use of correction fluid will not be permitted.

It will be the responsibility of the investigator to ensure the accuracy of all data entered in the CRFs. The delegation log will identify all those personnel with responsibilities for data collection and handling, including those who have access to the trial database.

The Case Report Forms will be designed to capture the data required to inform baseline comparisons of the groups, record safety parameters, and provide data for analysis of primary, secondary and safety endpoints as described in the protocol and statistical plan. Standard abbreviations will be used for missing data (NA, not available/applicable; ND, not done; UNK, unknown).

12.3 Data handling and analysis

Data relevant to patients' clinical care will be recorded and stored in a study folder, held on the ward, under the guardianship of the ward nursing staff caring for the patient. Data not relevant to the patients' clinical management will be held in a study folder, kept in a secure location away from the ward. All person-identifiable data held away from the ward—both during and after the study period—will be kept in a locked room within a card-accessed area of the University site, which is protected by 24-hour on-site security personnel and fire detection and alarm system.

Data will be transferred to an electronic database in the Excel software programme by double entry. The resulting databases will be compared to identify discrepancies, and subject to range checks to identify missing and spurious data. Such data will be corrected with reference to the Case Report Forms and, as necessary, to source documents (original clinical records, electronic records, observation records, electronic device records for capillary glucose and exacerbation of chronic pulmonary disease tool (EXACT) measurements, photographic records of skin blanch test results).

Electronic data will be kept in encrypted databases, on a restricted access area of the University computer network. This is backed up locally on a daily basis, and monthly backups are held securely in an offsite location. No patient identifiable data will be stored on laptop computers or portable storage devices, or will be sent by electronic mail. The computer network is protected by an intrusion detection system.

13 Archiving arrangements

The trial documents (including trial master file, case report forms and consent forms) will be kept for a minimum of five years. They will be stored in locked offices within the St George's, University of London site, or in an archiving site as recommended and/or approved by the Joint Research Office. The trial database will be kept electronically on the St George's, University of London computer network, for a minimum of five years.

14 Statistical methods

14.1 Statistical input in trial design

The trial design and statistical analysis plan have been constructed with input from [name], Senior Lecturer in Medical Statistics, St George's, University of London.

14.2 Endpoints

14.2.1 Primary endpoint

Mean capillary glucose concentration during hospitalisation period—defined as the mean of all capillary glucose measurements obtained according to the study protocol for that patient during the period between enrolment in the trial and hospital discharge. This measure has been evaluated against more complex endpoints (time-averaged glucose and hyperglycaemic index) and found to be the most practical metric of hyperglycaemia-associated risk.¹³

14.2.2 Secondary endpoints

Unless otherwise specified, the endpoints described below related to a comparison of data between the active treatment and placebo groups.

Clinical efficacy:

- COPD Assessment Test score at 4 weeks and, where available, at 12 weeks—defined as the sum of the points marked on the patient-completed COPD Assessment Test, as published; comparisons of mean score at follow-up and proportion of patients with improvement ≥ 5 points
- Exacerbation of Chronic Pulmonary Disease Tool (EXACT) scores—mean scores at days 5, 10 and 28
- time to medical fitness for discharge—defined as the number of days between study enrolment and the day on which the patient is documented by the clinical care team to be medically fit for hospital discharge, if this is different to the date of actual discharge
- time to actual discharge—defined as the number of days between study enrolment and the day on which the patient is discharged from the hospital
- rates of recurrent exacerbation, readmission, or death—defined, respectively as the number of days between study enrolment and the day on which the patient is prescribed a systemic antibiotic or steroid (for an exacerbation of COPD), is readmitted to hospital (for any reason except planned elective treatment or investigation), or dies (from any cause)

Glycaemic control:

- mean daily insulin use during hospitalisation period—defined as total number of units of insulin administered (of any formulation), divided by the duration of hospitalisation (in days)
- mean HbA1c and serum fructosamine concentration at follow-up, and change from baseline

Inflammation and infection:

- mean C-reactive protein concentration at discharge and follow-up (absolute values and change from baseline)
- a relevant panel of markers of inflammation and oxidative stress, measured on serum samples collected at study entry, discharge and follow-up (absolute values and change from baseline)

Other metabolic effects:

- mean body mass index at follow-up
- mean waist circumference at follow-up

Airflow limitation

- FEV₁ at 4 weeks—mean values at follow-up and mean change from discharge

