5.2 Secondary objectives

To determine whether, in patients hospitalised for COPD exacerbations and receiving conventional treatment, the addition of metformin, as compared with placebo, produces effects on clinical outcome, and measures of inflammation, steroid sensitivity, and airflow obstruction, which merit further study.

The data collected in relation to the secondary objectives will be hypothesis-generating. They will also be used to inform the selection of appropriate end points, and as a basis for sample size calculations, for a future larger study.

6 Trial design

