9.6 Summary flow chart of study assessments

Day	IMP administration	Assessments
1	One capsule	Capillary glucose concentration (thereafter repeated before and 2 hours after each mealtime, and at approximately 22:00) COPD Assessment Test (CAT) Exacerbations of Chronic Pulmonary Disease Tool (EXACT) Malnutrition Universal Screening Tool (MUST) Renal profile, liver profile, CRP, lactate, random glucose, HbA1c Serum sample saved
2	One capsule twice daily	Exacerbations of Chronic Pulmonary Disease Tool (EXACT) Capillary glucose (as above) CRP Food chart if admission MUST score 1 (medium risk)
3	Two capsules morning, one capsule evening	Exacerbations of Chronic Pulmonary Disease Tool (EXACT) Capillary glucose (as above) CRP measured daily to day 7 Food chart if admission MUST score 1 (medium risk)
Day 4 until discharge	Two capsules twice daily	Exacerbations of Chronic Pulmonary Disease Tool (EXACT) Capillary glucose (as above) CRP measured daily to day 7 Safety parameters (renal function, liver enzymes, plasma lactate, venous glucose) measured at least every 72 hours until day 7 (more often if deemed necessary by study team or clinical team), then at a frequency appropriate for the clinical condition of the patient (no less often than once-weekly)
Day of discharge	Two capsules twice daily	Capillary glucose (as above, until time of discharge) Exacerbations of Chronic Pulmonary Disease Tool (EXACT) COPD Assessment Test Spirometry CRP Serum sample saved
Day of discharge until follow-up	Two capsules twice daily	Exacerbations of Chronic Pulmonary Disease Tool (EXACT)
Follow-up (day 28–35)	Two capsules in the morning	Structured interview and pill count COPD Assessment Test (CAT) Weight, height and waist circumference Spirometry Venous glucose, HbA1c, lactate, CRP Serum sample saved
12 weeks	None	Vital status (electronic patient record) Hospital admissions (self-reported and electronic patient record) COPD Assessment Test (returned by post) Antibiotic and steroid courses (self-reported) Diagnosis and/or treatment for diabetes (self-reported)

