14.4 Statistical analysis plan

14.4.1 Summary of baseline data and flow of patients

The report will detail the number of eligible patients for the trial, the number consenting and the number randomised. A breakdown will be presented for each group of the numbers of participants assigned, receiving the intended treatment, completing the study protocol, and analysed for the primary outcome. This information will be displayed as a flow diagram.

The following data will be used to describe baseline comparability of study groups:

- Age (continuous)—mean and standard deviation

- Sex (categorical)—proportions
- COPD Assessment Test score (interval scale)—mean and standard deviation
- Exacerbation of Chronic Pulmonary Disease Tool score (interval scale)—mean and standard deviation
- Forced expiratory volume in 1 second (continuous)—mean and standard deviation
- Presence of radiographic consolidation (categorical, defined by the presence or absence of consolidation or airspace shadowing on a chest X-ray, as reported by a radiology specialist as part of routine clinical practice)—proportions
- Venous blood glucose concentration (continuous)—mean and standard deviation
- Haemoglobin A1c (continuous)—mean and standard deviation
- C-reactive protein concentration (continuous)—mean and standard deviation

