14.4.3 Secondary endpoint analysis

This study has not been powered for its secondary endpoints. The secondary analyses are for the purpose of hypothesis generation, rather than to provide firm conclusions. This study will inform the design of a future larger trial.

Means will be compared using the t-test (for normally-distributed continuous data), Mann-Whitney test (for non-normally-distributed continuous data), or Chi-square or Fisher's exact test as appropriate (for categorical data). Time-to-event data will be analysed and presented using Kaplan-Meier curves, the log rank test, and Cox proportional hazards regression.

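### Follow-up CAT is compared without adjustment for the scheduled Day 1 score, which gives up some precision, and the 5-point improvement has no stated reference time

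*Protocol*

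**What the plan says.** Protocol section 14.2.2 lists CAT under clinical efficacy, at 4 weeks and, where available, at 12 weeks. The outcome is expressed as "comparisons of mean score at follow-up and proportion of patients with improvement ≥ 5 points". No starting point is given for the improvement.

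Section 14.4.3 fixes the tests. "Means will be compared using the t-test (for normally-distributed continuous data"), with Mann-Whitney as the alternative when the data are not normal, and "Chi-square or Fisher's exact test as appropriate (for categorical data") for proportions. No covariate is mentioned, and section 14.4.5 plans no sensitivity or other analyses.

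The assessment table in section 9.6 includes "COPD Assessment Test (CAT) Exacerbations of Chronic Pulmonary Disease Tool (EXACT) Malnutrition Universal Screening Tool (MUST") among the Day 1 assessments. It schedules CAT again on the day of discharge, at the day 28–35 visit and at 12 weeks. In the analysis text, baseline CAT appears by name only in section 14.4.1, as a descriptor of group comparability: "COPD Assessment Test score (interval scale)—mean and standard deviation".

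Other secondary endpoints in section 14.2.2 do use an earlier value on the continuous scale. One example is "mean HbA1c and serum fructosamine concentration at follow-up, and change from baseline"; C-reactive protein and the serum markers also get change from baseline, and FEV₁ gets change from discharge.

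On status, section 14.4.3 says "This study has not been powered for its secondary endpoints". Section 5.2 gives the secondary data a further purpose: "They will also be used to inform the selection of appropriate end points, and as a basis for sample size calculations" for a later, larger study.

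**The concern.** When a score is measured before treatment and again at follow-up, the early score usually explains part of the spread between patients at follow-up. An unadjusted comparison leaves that spread in the error term. It also lets part of any chance baseline difference between arms pass into the estimate, and with about 23 placebo patients such differences are not negligible. Here the baseline is already scheduled, yet the only planned comparison that uses an earlier CAT value is a yes/no split, which is itself an inefficient use of the scale.

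This matters in a pilot because section 5.2 intends the secondary results to guide endpoint choice and sample size. What a planner takes from the CAT result is the estimate, its interval and the relevant SD. Adjustment would narrow the interval and report the residual SD directly.

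The missing reference time is a separate small gap. With CAT scheduled both on Day 1 and at discharge, the 5-point proportion can be computed in two ways that may give different answers.

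**Working it through.** **The plan's own figures.** The protocol gives no power or precision figure for CAT. Its only sample-size figures (section 14.3.1) are for glucose: SD 1.5, difference 1.5 mmol/L, two-sided alpha 0.05, 90% power. The normal formula gives 2 × (1.960 + 1.282)² × (1.5/1.5)² = 21.01, so 22 per arm, or 44. At 2:1 the control arm needs 1.5 × 10.51 = 15.8, so 16, with 32 on active, or 48. Both stated totals reproduce. By the non-central t distribution, power is 90.0% at 22/22 and 89.2% at 32/16.

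**Inputs for CAT.**
- 69 patients at 2:1 (section 14.3.1), taken as 46 versus 23. Section 14.5 notes that the final ratio cannot be predicted exactly.
- Two-sided alpha 0.05.
- Assumptions not in the documents: rho from 0.2 to 0.7; a true difference of 0.5 SD; SD 7 CAT points, equal at both times; no attrition.

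**Formulas.**
- Unadjusted standard error = SD × √(1/46 + 1/23) = 0.2554 SD.
- Adjusted variance ≈ unadjusted variance × (1 − rho²).
- Non-centrality = 0.5 / (0.2554 × √(1 − rho²)). Power is from the non-central t with 67 degrees of freedom; using 66 for the adjusted model changes it by less than 0.1 point.
- Half-width of the 95% CI = t × 7 × 0.2554 × √(1 − rho²), with t = 1.996 or 1.997.

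| rho | variance factor | non-centrality | power | half-width (CAT points) |
|---|---|---|---|---|
| unadjusted | 1.00 | 1.96 | 48.8% | 3.6 |
| 0.2 | 0.96 | 2.00 | 50.4% | 3.5 |
| 0.3 | 0.91 | 2.05 | 52.5% | 3.4 |
| 0.5 | 0.75 | 2.26 | 60.6% | 3.1 |
| 0.7 | 0.51 | 2.74 | 77.1% | 2.5 |

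The variance falls by 4%, 9%, 25% and 49% in turn. At rho 0, adjustment moves power only from 48.80% to 48.78%.

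**Chance imbalance.** The standard error of the Day 1 difference between arms is also 0.2554 SD, or 7 × 0.2554 = 1.8 points at SD 7. With equal SDs, about rho times an observed imbalance enters the unadjusted follow-up difference. For a one-standard-error imbalance that is about 0.5, 0.9 and 1.3 points at rho 0.3, 0.5 and 0.7.

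**A simple change score is not the remedy.** Its variance relative to the follow-up mean is 2(1 − rho): 1.40 at rho 0.3, 1.00 at 0.5 and 0.60 at 0.7. Below rho 0.5 it is worse than doing nothing, whereas the adjusted model is not, apart from one degree of freedom.

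**The 5-point split.** If the change in CAT is normal and a share p improves by 5 points or more, the large-sample efficiency of the proportion relative to the mean change is φ(c)²/[p(1 − p)], where c is the normal quantile of p. This is 0.64 at p = 0.5 and 0.49 at p = 0.2 or 0.8, so the split discards 36% to 51% of the information in the change score.

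**The case against.** The strongest reply is that nothing here is an error. Comparing follow-up means between randomised groups is valid and unbiased, and the protocol disclaims power and firm conclusions for all secondary endpoints. That stands, and it limits the point to efficiency.

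The size of the gain is also open. Day 1 CAT is taken during an acute exacerbation, and section 6.4 cites a study in which symptom scores had recovered by day 35 in 86.1% of exacerbations. That does not fix rho, but it gives no ground for presuming a high value. At rho 0.2 the power gain is under 2 points. This stands too.

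A reader might infer three stronger things that the documents do not support:

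- **That a baseline imbalance passes in full into the result.** Only about rho times the imbalance does.
- **That planning information for the larger trial is lost.** Day 1 and follow-up CAT are both scheduled for recording, so rho and the residual SD could be computed later. A raw follow-up SD would make that trial larger, not underpowered.
- **That CAT is the leading efficacy endpoint and is known for every patient at baseline.** Section 14.2.2 does not rank its endpoints, and section 9.6 shows what is scheduled, not what is complete.

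The 5-point proportion is reported alongside the mean, so the split takes nothing away from the continuous comparison. Its weakness is a reason not to lean on it, not a reason to drop it.

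It could also be said that adjustment belongs in a separate analysis plan. Section 14.4 of the protocol, however, is itself the statistical analysis plan section and names unadjusted tests, so this is a choice made here and not a detail left open.

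**Conclusion.** The point holds as a modest, nearly costless improvement to one exploratory endpoint. The protocol fixes an unadjusted comparison of follow-up CAT although a Day 1 score is scheduled for all participants. Adjustment would cut the variance of the difference by about rho². Under the stated assumptions (46 versus 23, no attrition, a 0.5 SD difference, SD 7), power rises from 49% to between 50% and 77%, and the CI half-width falls from 3.6 to between 3.5 and 2.5 points, over rho 0.2 to 0.7. The documents do not say where in that range rho lies, and the low end is plausible. Drop-out, put at about 5% in section 14.3.1, and incomplete 12-week returns would lower both power figures.

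The missing reference time for the 5-point improvement needs no assumption: the text names none, and two earlier CAT assessments are available. Neither matter biases the trial or touches the primary glucose analysis.

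**What to change.** In sections 14.2.2 and 14.4.3:

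- Analyse CAT at 4 weeks, and at 12 weeks where available, by a linear model of the follow-up score on treatment with Day 1 CAT as covariate.
- Report the adjusted difference, its 95% CI and the residual SD.
- Keep the proportion improving by at least 5 points as a descriptive summary, and state that improvement is counted from Day 1, or name the reference time intended.
- State how a missing Day 1 CAT is handled, for example mean imputation of the covariate or exclusion from this model.

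The cost is wording, one degree of freedom and that short missing-data rule. No new assessment is needed. If the change is made after the analysis plan was finalised, section 14.7 requires it to be reported and justified.

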In this study, we consider there to be a risk of lactic acidosis related to the underlying condition (COPD) and commonly associated comorbidities (such as respiratory failure, heart failure, renal failure and severe sepsis). As noted above, the lactate levels and prognosis observed in cases of lactic acidosis are believed to be dictated by with the severity of the underlying condition, rather than to the presence or plasma concentration of metformin.^{40,68} Nevertheless, given the lack of certainty over the safety of metformin therapy in such settings, and to avoid potential confusion over the aetiological agent, we shall stop or suspend the study drug if a condition develops in which there is a high risk of lactic acidosis, or if the plasma lactate concentration rises above pre-specified levels.

Further, we consider that there is a small but genuine risk of metformin-associated lactic acidosis if metformin is allowed to accumulate due to renal failure. To mitigate this, we will monitor the renal function regularly while the participant is an inpatient (when, due to the severity of their concurrent illnesses, the risk of developing renal failure is greatest), and stop or suspend the study treatment if the estimated GFR falls, or the serum creatinine rises, above pre-specified levels.

We judge that the risk of metformin-associated lactic acidosis outside the situations described above is extremely low. This risk must be balanced against the seriousness of the condition under study. As noted above, the 90-day mortality rate following hospitalisation for a COPD exacerbation is 13.9%; the 5-year mortality rate exceeds 50%. Observational data suggest that

lowering blood glucose concentration may offer the prospect of substantial benefit. As such, our assessment is that the risk–benefit balance lies in favour of undertaking this trial.

5 Study objectives

The overarching research question for this body of work is to ascertain whether metformin improves recovery from COPD exacerbations. This pilot study will address two more limited questions, as a basis for future trial design.

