6.4 Treatment period

[figure not shown]
The duration of hospitalisation for COPD exacerbations is variable. In a study conducted in this hospital,¹⁴ the median length of stay was 9 days (interquartile range, 5–17 days). In a more recent audit and service evaluation study in this hospital, of patients with diabetes and COPD exacerbations, the median length of stay was 8 days (interquartile range, 4–16 days; range 0–75 days). To avoid the introduction of bias (whereby, for example, individuals who were less unwell and thus had a shorter stay would have a lower exposure to the study drug), we have elected to adopt a standardised treatment period for all participants. A period of 28–35 days was selected, to capture the full duration of hospitalisation for the considerable majority of patients, and most of the recovery period. In a prospective study of 91 patients, who experienced 504 exacerbations, the total symptoms score had recovered by day 35 in 86.1% of exacerbations. A 7-day period of leeway was selected to take account of potential difficulties arranging a follow-up appointment (due to weekends, public holidays, and patient/staff availability), while ensuring that the study drug can be continued until the date of that appointment. Follow-up appointments will take place at the site of recruitment.

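### EXACT is scheduled from day 1 through the outpatient phase, but the plan compares three single-day means without the day-1 score, which loses precision on a measure meant to help plan the next trial

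*Protocol*

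**What the plan says.** - **Collection.** The flow chart in section 9.6 lists EXACT on days 1, 2 and 3, from day 4 to discharge, on the day of discharge, and from discharge until follow-up. Daily completion is implied by these rows but not written out, and the day 28–35 follow-up row does not list EXACT. Section 12.3 names as a source "electronic device records for capillary glucose and exacerbation of chronic pulmonary disease tool (EXACT) measurements".
- **Endpoint.** Section 14.2.2 defines the EXACT endpoint as "mean scores at days 5, 10 and 28". It defines no average over time, slope or time to symptom recovery from this series.
- **Test.** Section 14.4.3 compares means by a t-test or, for non-normal data, a Mann-Whitney test. Section 14.4.5 plans no sensitivity or other analyses.
- **Baseline.** Section 14.4.1 summarises the EXACT score at baseline to describe the groups. Section 14.2.2 asks for change from baseline for HbA1c, fructosamine, C-reactive protein and the serum markers, but not for EXACT.
- **Purpose.** Section 5 gives the overarching aim as "to ascertain whether metformin improves recovery from COPD exacerbations" and limits this pilot to two narrower questions. On the secondary data, section 5.2 says: "They will also be used to inform the selection of appropriate end points", and also names them as a basis for sample size. Section 14.4.3 adds: "This study has not been powered for its secondary endpoints".

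**The concern.** EXACT is the one symptom score scheduled repeatedly across both the inpatient and the outpatient phase. Patients enter an exacerbation with very different symptom levels, and much of the spread at day 5 or day 10 is likely to be spread that was already there on day 1. A comparison of raw means on a single day leaves all of it in the error term. It also uses one reading per patient where many are scheduled.

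The primary glucose analysis is untouched. What is at stake is the planning use in section 5.2: a noisy estimate of the EXACT difference, with a standard deviation that ignores baseline, is a poor basis for deciding whether EXACT should be an endpoint of the next trial and how large that trial must be.

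**Working it through.** **The plan's own figure.** The only sample size calculation is for glucose (section 14.3.1), and it reproduces. A difference of 1.5 with SD 1.5, 90% power and two-sided 0.05 needs 22 per arm, 44 in all; 32:16 (48) gives 89%. There is no corresponding figure for EXACT, so what follows is an illustration on assumed inputs.

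**Inputs.**
- From the protocol: 69 patients at 2:1, taken as 46 and 23; two-sided 0.05.
- Assumed: 15-point excess on day 1 in both arms; exponential recovery; between-patient SD 8; day-to-day SD 6 with lag-one correlation 0.5; no missing days.
- Assumed time constants in days, placebo v metformin: 10 v 5, 10 v 6, 20 v 10 and 20 v 12.

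**Day 10 (10 v 5).**
- True difference: 15 × (exp(−9/10) − exp(−9/5)) = 15 × (0.407 − 0.165) = 3.62 points.
- Single-day SD: √(64 + 36) = 10. SE = 10 × √(1/46 + 1/23) = 2.55.
- Difference/SE = 1.42, giving power of about 28%.
- Correlation of day 10 with day 1: (64 + 36 × 0.5⁹)/100 = 0.64. Adjusted SE ≈ 2.55 × √(1 − 0.64²) = 1.96. Difference/SE ≈ 1.85, giving power of about 44%.

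**Mean of days 2–14 (10 v 5).**
- True difference: 3.16 points.
- Variance of the mean: 64 + 36 × 0.207 = 71.5, so SD 8.45 and SE 2.16. Unadjusted power is about 30%, hardly more than day 10 alone.
- Correlation with day 1: 0.79. Adjusted SE ≈ 2.16 × √(1 − 0.79²) = 1.32. Difference/SE ≈ 2.39, giving power of about 65%.

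**Power by simulation (4,000 trials per scenario; repeat runs differ by up to about 2 points).**

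| Analysis | 10 v 5 | 10 v 6 | 20 v 10 | 20 v 12 |
|---|---|---|---|---|
| Day 5, unadjusted | 25% | 15% | 15% | 10% |
| Day 10, unadjusted | 28% | 19% | 26% | 17% |
| Day 28, unadjusted | 7% | 6% | 20% | 15% |
| Day 10, adjusted for day 1 | 44% | 29% | 40% | 24% |
| Mean of days 2–14, unadjusted | 30% | 20% | 24% | 16% |
| Mean of days 2–14, adjusted | 65% | 42% | 52% | 31% |
| Mean of days 2–28, adjusted | 46% | 31% | 65% | 42% |

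**Reading.**
- Averaging alone gains almost nothing, because the stable between-patient spread remains. The day-1 score removes most of that spread, and averaging then helps.
- The gain depends on the correlation with day 1. For a single day the SE factor is √(1 − ρ²): 0.95 at ρ = 0.3, 0.87 at 0.5 and 0.77 at 0.64.
- No window is best throughout: days 2–14 wins under fast recovery, days 2–28 under slow.

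**Are the chosen days badly placed?** Under 10 v 5 the difference peaks at 3.75 points near day 8. Day 5 has 3.31 (88% of the peak), day 10 has 3.62 (97%) and day 28 has 0.94 (25%). Under 20 v 10, day 28 keeps 2.88 of 3.75 (77%).

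**The case against.** The strongest reply is that nothing here is misstated. The secondary endpoints are openly unpowered and hypothesis-generating, and recovery is also measured by time to medical fitness, time to discharge and CAT improvement, with time-to-event methods in section 14.4.3. The repeated EXACT records will still exist when the next trial is planned. All of that stands, and it keeps the severity low. It does not remove the point: the protocol itself fixes the endpoint and the test, and choosing endpoints and sizing a later trial is a stated use of the result. The discharge measures also depend on care-team decisions, which a symptom score does not.

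A reader might go further and infer that the three days are the least informative ones. The working does not support that. Day 10 is close to the largest separation in all four scenarios, and day 28 is weak only if recovery is fast.

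A reader might also infer from section 6.4, where "the total symptoms score had recovered by day 35 in 86.1% of exacerbations", that most patients in either arm will have recovered by day 28. That figure is for day 35, comes from an external cohort and counts exacerbations recovered. It gives no score trajectory, no day-28 share and nothing by arm. Nor is the 4-week CAT comparison an error: it records status at the end of treatment.

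**Conclusion.** The point holds as a cheap improvement of low severity. The protocol compares EXACT on three single days by an unadjusted test although a day-1 score and a repeated series are scheduled, and this gives up precision. Under the assumed parameters, day-1 adjustment alone takes day-10 power from about 28% to 44% (26% to 40% under slower recovery). An adjusted mean over a suitable window reaches about 65% where the assumed time constant is halved, and about 42% for the smaller effects.

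The direction rests on a reasonable correlation between day-1 and later scores; the size rests on assumed EXACT means, SDs, correlations and recovery speeds, none of which the protocol gives. The main loss comes from leaving out the day-1 score rather than from the choice of days, and the primary endpoint is not affected.

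**What to change.** In sections 14.2.2 and 14.4.3, compare EXACT between arms with the day-1 score as covariate, using one pre-specified summary of the scheduled series. Either a repeated-measures model with a named contrast or the mean over a window fixed before unblinding would serve. Keep days 5, 10 and 28 as adjusted or descriptive time points.

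The cost is wording and modest analysis, with no new visits or data. There are two downsides. The window must be chosen without knowing recovery speed: under 10 v 5, days 2–28 gives 46% against 65% for days 2–14, and under 20 v 10 the order reverses (65% against 52%). Missing diary days would bias or complicate a simple mean, so where they are more than occasional the repeated-measures version is needed. If enrolment has begun, section 14.7 requires the change to be reported and justified.
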